11.3.3.3. Cytokine Release Syndrome Treatment Guidelines by Grade

The following are treatment guidelines for XmAb18087 treatment-related infusion reactions (Lee, 2019); since it can be difficult to differentiate between different infusion reaction etiologies, both are included here.

Grade 1:

- Administer acetaminophen and/or diphenhydramine or dexamethasone to treat signs and symptoms if clinically indicated.
- Vital signs should be measured every 15 minutes or less as clinically indicated.
- Obtain a blood sample for cytokine analysis during the event and approximately 4 hours later, unless to scheduled cytokine monitoring is already in progress.

Version 1.0 Page 89 of 145

- Monitor the subject for worsening of condition; if severity of event increases to a higher grade, stop the infusion, administer appropriate treatment, and refer to guidelines below for more severe infusion reactions.
- It may be useful to premedicate the subject with acetaminophen and antihistamines prior to the next infusion.

Grade 2:

- Hypotension responsive to fluids or a low dose of a single pressor, or mild respiratory symptoms treatable with low-flow oxygen are signs of Grade 2 toxicity. Older subjects or those with significant comorbidities may be at higher risk of decompensation in this situation.
- **Discontinue the infusion** and administer acetaminophen and/or diphenhydramine or dexamethasone to treat signs and symptoms if clinically indicated. Once symptoms have resolved, slow the infusion rate by 50% of the baseline rate. If after 1 hour, the subject's symptoms do not return and vital signs are stable, the infusion rate may be increased every 30 minutes, as tolerated, to the baseline rate.
- Note that older subjects or those with significant comorbidities may be at higher risk of decompensation in this situation. When reactions occur in these vulnerable subjects, or in the case of rapidly escalating reactions, consider treatment with **tocilizumab** 4 to 8 mg/kg IV over 1 hour, with or without dexamethasone 10 to 20 mg IV (or equivalent).
- Vital signs should be measured every 15 minutes or less as clinically indicated. For subjects who are able to tolerate an increase in the infusion rate back to baseline and maintain normal blood pressure for 30 minutes after the rate increase then, at the discretion of the Investigator, the frequency of vital sign assessment may be reduced to every 30 minutes during the infusion.
- Obtain a blood sample for cytokine analysis during the event and approximately 4 hours later, in addition to scheduled cytokine monitoring if already in progress.
- Monitor the subject for worsening of condition; if severity of event increases to a higher grade, stop the infusion, administer appropriate treatment, and refer to guidelines below for Grades 3 and 4 infusion reactions.
- Subjects with maximum Grade 2 infusion reaction may continue on study and should receive prophylactic premedication with acetaminophen 650 mg PO and diphenhydramine hydrochloride 25 to 50 mg IV or PO prior to all subsequent XmAb18087 infusions.

Grade 3 and 4:

- Stop the infusion and disconnect the infusion tubing from the subject.
- Aggressive supportive care should be given immediately. Vasopressors, fluids, oxygen, epinephrine or bronchodilators, ventilatory support, antipyretics, and analgesics should be used as indicated.

Version 1.0 Page 90 of 145

- Treatment with tocilizumab 4 to 8 mg/kg IV over 1 hour with or without dexamethasone 10 mg IV (or equivalent) is strongly encouraged for CRS due to the high risk of progression and permanent organ dysfunction.
- Hospital admission for observations is almost always indicated, usually to an intensive care unit, since an initial appearance of improvement may quickly yield to rapid decompensation.
- Subjects with Grade 3 CRS or infusion reaction may be rechallenged once resolved. Subjects with recurrent Grade 3 or any Grade 4 infusion reaction should not receive further XmAb18087 treatment but will continue to be followed on the protocol (ie, for 4 weeks after last dose).
- Obtain a blood sample for cytokine analysis during the event and approximately 4 hours later, in addition to scheduled cytokine monitoring if already in progress.
- Obtain a sample for ADA testing as close to the onset of the event as possible, at the resolution of the event, and 28 days following the event.
- Notify the Xencor Safety Monitor or Xencor Medical Monitor, (Telephone: ; Email:), immediately.

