7.8. Criteria for Adverse Events of Specific Concern and Dose Adjustment

The National Cancer Institute's (NCI's) Common Terminology Criteria for Adverse Events (CTCAE), Version 5.0, will be used for grading toxicities, except for CRS, which will be graded using the CRS revised grading system (Section 11.2 or Appendix C; Lee, 2014).

An AESC is defined as an AE or clinically significant abnormal laboratory value (unless clearly attributable to underlying malignancy or concurrent disease) occurring after the initiation of dosing and meeting the criteria listed below:

For Parts A, B, and C:

1. Any Grade 5 toxicity

Version 1.0 Page 51 of 145

- 2. Grade \geq 3 thrombocytopenia lasting \geq 7 days or \geq Grade 3 thrombocytopenia of any duration if associated with \geq Grade 3 bleeding
- 3. Grade 4 neutropenia or Grade 3 febrile neutropenia lasting ≥ 7 days, or Grade 4 febrile neutropenia
- 4. Any \geq Grade 3 nonhematological toxicity, **except**:
 - a. Grade 3 fatigue, asthenia, fever, anorexia, or constipation
 - b. Grade 3 nausea, vomiting, diarrhea, or abdominal pain controlled by medical management that decreases to \leq Grade 2 within \leq 7 days
 - c. Grade 3 alanine aminotransferase (ALT) and/or aspartate aminotransferase (AST) that decrease to \leq Grade 2 within \leq 5 days
 - d. Grade ≥ 3 gamma glutamyl transferase (GGT), unless it occurs with AST, ALT, and/or total bilirubin values that meet AESC criteria
 - e. Grade 3 electrolyte abnormalities that are clinically insignificant, or treatable, and that resolve, with or without intervention, to < Grade 2 in < 72 hours
 - f. Grade 3 or 4 lipase values that are not accompanied by ≥ Grade 3 amylase values or clinical symptoms or radiographic evidence of pancreatitis

Additional Criterion for Part B (combination therapy) only:

1. Any immune related adverse event (IRAE) that requires permanent discontinuation of study drug according to the guidelines in Table 18

Subjects who experience any toxicity should be followed until the toxicity stabilizes or has returned to their baseline level, or until the commencement of a new anticancer treatment.

Refer to Section 10.3 for safety criteria for adjustment or stopping XmAb18087 and pembrolizumab.

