11.3.2. Cytokine Release Syndrome Versus Allergic or Hypersensitivity Reactions

Cytokine release syndrome is mechanistically different from allergic/hypersensitive reactions (Lee, 2019), although some of the manifestations are common to both AEs and both have been reported to occur with therapeutic antibodies. An acute infusion reaction is often caused by a type 1 hypersensitivity mechanism due to immunoglobulin-E (IgE)-mediated release of histamines and prostaglandins, although a direct interaction with mast cells and basophils can also occur. It is less clear how cytokine release is triggered, although it is likely to be associated with immune cell activation; in this case, there is evidence that immunologic cascade is initiated by triggering of CD3-expressing T lymphocytes, resulting in TNF- α mediated monocyte/macrophage activation and systemic toxic cytokine release (Li, 2019).

Signs and symptoms usually develop during or shortly after drug infusion in hypersensitivity reactions, are more likely to occur after several doses of the drug and are largely related to histamine release. Typical signs and symptoms of hypersensitivity reaction include rash/urticaria, flushing, pruritus, fever, dyspnea, cough, and hypotension, although the following may also occur (Lenz, 2007):

Arthralgia

Version 1.0 Page 87 of 145

^a Fever is defined as temperature ≥ 38 °C not attributable to any other cause. In patients who have CRS then receive antipyretic or anticytokine therapy such as tocilizumab or steroids, fever is no longer required to grade subsequent CRS severity. In this case, CRS grading is driven by hypotension and/or hypoxia.

^b CRS grade is determined by the more severe event: hypotension or hypoxia not attributable to any other cause. For example, a patient with temperature of 39.5 °C, hypotension requiring 1 vasopressor, and hypoxia requiring low-flow nasal cannula is classified as grade 3 CRS.

^c Low-flow nasal cannula is defined as oxygen delivered at \leq 6 L/minute. Low flow also includes blow-by oxygen delivery, sometimes used in pediatrics. High-flow nasal cannula is defined as oxygen delivered at \geq 6 L/minute.

- Bronchospasm
- Confusion, mental status changes, and/or delirium
- Dizziness
- Fatigue (asthenia, lethargy, malaise)
- Hallucinations
- Headache
- Hypertension
- Myalgia
- Nausea and/or vomiting
- Rigors/chills
- Diaphoresis
- Tachycardia

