All sites should review and implement the general guidelines for the use of tocilizumab and IV fluids discussed below. Otherwise, management of CRS and other infusion-related reactions

Version 1.0 Page 121 of 145

should be per standard investigational site procedures. Or, if there are no local standards or if they are incomplete, the approaches discussed here may be used.

CONFIDENTIAL

Table 15. American Society for Transplantation and Cellular Therapy Cytokine Release Syndrome Consensus Grading

CRS Parameter	Grade 1	Grade 2	Grade 3	Grade 4
Fever ^a	Temperature ≥ 38 °C	Temperature ≥ 38 °C	Temperature ≥ 38 °C	Temperature ≥ 38 °C
		With		
Hypotension	None	Not requiring vasopressors	Requiring a vasopressor with or without vasopressin	Requiring multiple vasopressors (excluding vasopressin)
		And/or ^b		
Hypoxia	None	Requiring low-flow nasal cannula ^c or blow-by	Requiring high-flow nasal cannula ^c , facemask, nonrebreather mask, or Venturi mask	Requiring positive pressure (eg, CPAP, BiPAP, intubation and mechanical ventilation)

BiPAP = bilevel positive airway pressure; CPAP = continuous positive airway pressure; CRS = cytokine release syndrome; CTCAE = Common Terminology Criteria for Adverse Events.

Organ toxicities associated with CRS may be graded according to CTCAE v5.0, but they do not influence CRS grading.

Cytokine Release Syndrome Versus Allergic or Hypersensitivity Reactions

Cytokine release syndrome is mechanistically different from allergic/hypersensitive reactions (Lee, 2014), although some of the manifestations are common to both AEs and both have been reported to occur with therapeutic antibodies. An acute infusion reaction is often caused by a type 1 hypersensitivity mechanism due to IgE-mediated release of histamines and prostaglandins, although a direct interaction with mast cells and basophils can also occur. It is less clear how cytokine release is triggered, although it is likely to be associated with immune cell activation; in this case, there is evidence that immunologic cascade is initiated by triggering of CD3-expressing T lymphocytes, resulting in TNF-α mediated monocyte/macrophage activation and systemic toxic cytokine release (Li, 2019).

Signs and symptoms usually develop during or shortly after drug infusion in hypersensitivity reactions, are more likely to occur after several doses of the drug and are largely related to histamine release. Typical signs and symptoms of hypersensitivity reaction include rash/urticaria,

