- Sufficient tocilizumab (dose of 8 mg/kg) should be readily available to the area where subjects are receiving their infusions and being observed post infusion.
- Prompt tocilizumab therapy should be strongly considered if:
 - Oxygen saturation falls below 90% on room air, **OR**
 - Systolic blood pressure falls 20 mm Hg below predose measurements and below 100 mm Hg, **OR**
 - Temperature of > 38 °C (100.4 °F) in the presence of new or worsening dyspnea and/or tachypnea and/or rigors and/or tachycardia (HR > 110 bpm), OR
 - Early discovery of hepatic transaminase elevation. (Note that peak transaminase elevation appears to occur within 24 hours, so that it is unlikely that tocilizumab treatment on the day after study drug administration would affect the course or outcome in the absence of concurrent symptoms or signs of CRS).
- Repeat dosing of tocilizumab may be necessary if signs and symptoms persist or return after initial treatment.

Fluid Management

Cytokine release syndrome is sometimes associated with myocardial dysfunction, pulmonary edema, or capillary leak syndrome (Shimabukuro-Vornhagen, 2018). Although there are little or no data regarding use of anti-CD3 antibodies and the need for fluid management, it seems prudent to monitor subjects for weight gain and limit IV fluid administration in the acute setting.

- If a subject is noted to have had a ≥ 10% increase in body weight over the previous 2 weeks in association with new or significantly increased bilateral lower extremity edema, dosing should be delayed until this finding is evaluated and, if indicated, treated
- For acute hypotension, an IV fluid bolus should be limited to 500 mL of normal saline or the equivalent.
- If there is not an adequate response to fluids, treatment with tocilizumab (and vasopressors, if necessary) should be considered rather than additional fluid boluses.

Cytokine Release Syndrome Treatment Guidelines by Grade

The following are treatment guidelines for XmAb18087 treatment-related infusion reactions (Lee, 2014); since it can be difficult to differentiate between different infusion reaction etiologies, both are included here.

Grade 1:

- Administer acetaminophen and/or diphenhydramine or dexamethasone to treat signs and symptoms if clinically indicated.
- Vital signs should be measured every 15 minutes or less as clinically indicated.

Version 1.0 Page 124 of 145

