- Obtain a blood sample for cytokine analysis during the event and approximately 4 hours later, unless scheduled cytokine monitoring is already in progress.
- Monitor the subject for worsening of condition; if severity of event increases to a higher grade, stop the infusion, administer appropriate treatment, and refer to guidelines below for more severe infusion reactions.
- It may be useful to premedicate the subject with acetaminophen and antihistamines prior to the next infusion.

Grade 2:

- Hypotension responsive to fluids or a low dose of a single pressor, or mild respiratory symptoms treatable with low-flow oxygen are signs of Grade 2 toxicity. Older subjects or those with significant comorbidities may be at higher risk of decompensation in this situation.
- **Discontinue the infusion** and administer acetaminophen and/or diphenhydramine or dexamethasone to treat signs and symptoms if clinically indicated. Once symptoms have resolved, slow the infusion rate by 50% of the baseline rate. If after 1 hour, the subject's symptoms do not return and vital signs are stable, the infusion rate may be increased every 30 minutes, as tolerated, to the baseline rate.
- Note that older subjects or those with significant comorbidities may be at higher risk of decompensation in this situation. When reactions occur in these vulnerable subjects, or in the case of rapidly escalating reactions, consider treatment with **tocilizumab** 4 to 8 mg/kg IV over 1 hour, with or without dexamethasone 10 to 20 mg IV (or equivalent).
- Vital signs should be measured every 15 minutes or less as clinically indicated. For subjects who are able to tolerate an increase in the infusion rate back to baseline and maintain normal blood pressure for 30 minutes after the rate increase then, at the discretion of the Investigator, the frequency of vital sign assessment may be reduced to every 30 minutes during the infusion.
- Obtain a blood sample for cytokine analysis during the event and approximately 4 hours later, in addition to scheduled cytokine monitoring if already in progress.
- Monitor the subject for worsening of condition; if severity of event increases to a higher grade, stop the infusion, administer appropriate treatment, and refer to guidelines below for Grades 3 and 4 infusion reactions.

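### CRS hypotension needing a low dose of one vasopressor is Grade 3 on the designated scale but Grade 2 in the treatment text, and the AESC section does not clearly direct grading to that scale

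*Protocol*

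**What the plan says.** **The designated scale.** Protocol Section 11.3.1, the introduction to Appendix C and SAP Section 11.1 all name ASTCT consensus grading for CRS. Table 10 and its copy, Table 15, allow Grade 2 hypotension only when no vasopressor is needed. Grade 3 is "Requiring a vasopressor with or without vasopressin". Footnote b of both tables gives an example: "hypotension requiring 1 vasopressor, and hypoxia requiring low-flow nasal cannula is classified as grade 3 CRS".

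**The treatment text.** The by-grade guidelines in Section 11.3.3.3 state that hypotension controlled by "fluids or a low dose of a single pressor, or mild respiratory symptoms treatable with low-flow oxygen are signs of Grade 2 toxicity". Appendix C repeats this: "Hypotension responsive to fluids or a low dose of a single pressor". These guidelines also cover infusion reactions other than CRS. The same introductory sentence cites a 2019 source in Section 11.3.3.3 ("2019); since it can be difficult to differentiate between different infusion reaction etiologies") and a 2014 source in Appendix C ("2014); since it can be difficult to differentiate between different infusion reaction etiologies").

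**The AESC definition.** Section 7.8 grades toxicity by CTCAE except for CRS, "which will be graded using the CRS revised grading system (Section 11.2 or Appendix C", and cites the 2014 source. Sections 7.9.1.1 and 7.9.3.1 use the same label. Section 10.1.3 gives the same Section 11.2 reference for CRS treatment. Section 11.2 is about IND safety reports and contains neither a scale nor treatment guidance.

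**The concern.** One CRS event can be given two grades depending on which page the site reads, and the two grades fall on either side of the AESC threshold. Section 7.8 counts nonhematological toxicity of Grade 3 or higher as an AESC, and CRS is not among its exceptions. CRS incidence and severity is part of the primary safety endpoint (Protocol Section 14.3.1) and remains a safety endpoint in SAP Section 3.3. The AESC count drives the run-in rule in Section 7.7 and the expansion boundaries in Section 7.8.2. The grade also determines what happens at the bedside. The Grade 2 guidance allows a paused infusion to restart at half rate once symptoms resolve. The Grade 3 guidance is to stop and disconnect, notify the sponsor's monitor at once, take anti-drug antibody samples, and give no further drug if a Grade 3 reaction recurs.

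**Working it through.** The plan gives no figure on this point, so the check is a comparison of texts followed by a reading of the rules.

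**1. Scope.** The comparison covers only events that meet the CRS definition. Under Table 10 footnote a, that means fever of at least 38 °C with no other cause. After antipyretic or anticytokine treatment, "fever is no longer required to grade subsequent CRS severity".

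**2. Side by side.**

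| Finding in a CRS event | Tables 10 and 15 | By-grade text (11.3.3.3, Appendix C) |
|---|---|---|
| Hypotension, no vasopressor | Grade 2 | Grade 2 (responsive to fluids) |
| Hypoxia, low-flow oxygen | Grade 2 | Grade 2 |
| Hypotension, low dose of one vasopressor | Grade 3 | Grade 2 |

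**3. Can the third row be reconciled?** Not by dose, because the tables set no minimum vasopressor dose. The footnote b example combines one vasopressor with low-flow oxygen. Low-flow oxygen alone is Grade 2, so the vasopressor is what makes the example Grade 3. The by-grade text lists both findings as Grade 2.

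**4. Following Section 7.8.** Section 11.2 holds no scale. Appendix C holds Table 15 and, later, the conflicting sentence. If 11.2 is a slip for 11.3, that section also holds both. The 2014 scale is not printed in the documents, so nothing can be said about how it would grade this event.

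**5. What one misgraded event does.** Let c be the true AESC count, one AESC per subject, and suppose one is read as Grade 2, so the recorded count is c − 1.

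- Run-in, first 3 subjects (Section 7.7): c = 1 read as 0 sends the cohort to the Safety Review Committee with 3 subjects instead of 3 + 3 = 6. c = 2 read as 1 enrolls 3 more instead of holding enrollment.
- Expansion (Tables 5 and 6): enrollment is suspended when the count reaches the boundary, which is 3 at n = 3 to 5 and 4 at n = 6. A count equal to the boundary, read as one lower, does not suspend.
- Dosing (Section 10.3.1): the AESC hold is not applied. It is released on recovery to baseline or to Grade 2 or lower, so a short event might delay no weekly dose.

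**6. The realised study.** SAP Section 5.1 gives 2 subjects in Part A and 2 in Part C, so 2 + 2 = 4. No part reached the 3 subjects at which the 3-versus-6 rule and the first boundary start to apply. The hold after 2 AESC could have applied only if both subjects in a part had one in the same cohort, and the documents report no such events. What can still be affected is the recorded CRS grade in at most 4 subjects.

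**The case against.** The strongest reply is that the documents already say which text grades CRS. Section 11.3.1 and Appendix C designate ASTCT and refer to the tables for the definitions, SAP Section 11.1 names the same scale, and a reader sent to Appendix C meets Table 15 before the treatment text. The conflicting phrase sits in management guidance that largely yields to site procedures. Section 11.3.2 and Appendix C also tell sites to contact the Medical Monitor immediately if the grade or treatment of a reaction is in question, and the Safety Review Committee reviews all available safety data. CRS in the first-in-human study was mostly low grade (Section 5.1.7).

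Most of this stands. A reader might infer that the plan leaves CRS with two competing scales. It does not: there is one designated scale and one inconsistent phrase. But the phrase assigns a grade under a CRS heading, and Section 7.8 neither names ASTCT nor points to Table 10. The instruction to call the Medical Monitor helps only a site that notices the question, and one reading just the Grade 2 text has no reason to ask. Under Section 11.1.2.1 the investigator assigns severity, and the SAP describes no re-derivation, so a wrong grade could pass into the listings.

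The objection is also right about the remedy. Deleting the phrase outright would change guidance for non-CRS infusion reactions, which are graded by CTCAE, and nothing in the documents shows the phrase to be wrong for them.

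**Conclusion.** The contradiction is real for events that meet the CRS definition. Hypotension needing a low dose of one vasopressor is Grade 3, and hence an AESC, on the designated scale, but Grade 2 in the treatment text. Section 7.8 does not send the reader cleanly to the scale.

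The practical size is small. No frequency is given for such events and it may be zero, so no effect on AESC rates or boundary-crossing probabilities can be claimed. The realised effect is confined to the CRS grades recorded for at most 4 subjects. A reader might infer that dose escalation or the expansion stopping rules were distorted. The documents do not support that: the 3-versus-6 rule and the Table 5 and 6 boundaries were never reached, and the output is listings only.

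The conclusion assumes that a site might grade from the treatment text without consulting the table or the Medical Monitor. The documents make that possible; they do not show that it happened.

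**What to change.** - **Grade 2 text in Section 11.3.3.3 and Appendix C:** state that for CRS the grade is set by Table 10 or 15 and that any vasopressor requirement is at least Grade 3 (Grade 4 for multiple vasopressors as the tables define it), so the low-dose single-pressor wording does not apply to CRS. Leave it in place for other infusion reactions.
- **Section 7.8:** replace the scale label, the Section 11.2 or Appendix C reference and the 2014 citation with ASTCT grading, Section 11.3.1 and Table 10.
- **Sections 7.9.1.1 and 7.9.3.1:** correct the scale label in the same way.
- **Section 10.1.3:** change the Section 11.2 reference to Section 11.3.
- **Before the listings are produced:** check any recorded CRS grades in the 4 subjects against Table 10. Concomitant medications are recorded on the eCRF (Section 9.2), so vasopressor use should be traceable.

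The cost is wording in six protocol places and a check of at most 4 subjects. The wording changes would need IRB review as an amendment (Section 17.1) and matter mainly if the text is reused. With the study terminated, the grade check is the only step that can change its output.

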11.3.1. Introduction and Grading

Grading of toxicity, including allergic/hypersensitivity reactions, is by CTCAE version 5.0, except for CRS, which is graded using the American Society for Transplantation and Cellular Therapy (ASTCT) CRS Consensus Grading (Lee, 2019) See Table 10 for these definitions.

All sites should review and implement the general guidelines for the use of tocilizumab and IV fluids discussed below in Sections 11.3.3.1 and 11.3.3.2. Otherwise, management of CRS and other infusion-related reactions should be per standard investigational site procedures. Or, if there are no local standards or if they are incomplete, the approaches discussed here may be used.

Version 1.0 Page 86 of 145

Table 10: American Society for Transplantation and Cellular Therapy Cytokine Release Syndrome Consensus Grading

CRS Parameter	Grade 1	Grade 2	Grade 3	Grade 4	
Fever ^a	Temperature ≥ 38 °C	Temperature ≥ 38 °C	Temperature ≥ 38 °C	Temperature ≥ 38 °C	
			With		
Hypotension	None	Not requiring vasopressors	Requiring a vasopressor with or without vasopressin	Requiring multiple vasopressors (excluding vasopressin)	
			And/or ^b		
Нурохіа	None	Requiring low-flow nasal cannula ^c or blow-by	Requiring high-flow nasal cannula c, facemask, nonrebreather mask, or Venturi mask	Requiring positive pressure (eg, CPAP, BiPAP, intubation and mechanical ventilation)	

BiPAP = bilevel positive airway pressure; CPAP = continuous positive airway pressure; CRS = cytokine release syndrome; CTCAE = Common Terminology Criteria for Adverse Events.

Organ toxicities associated with CRS may be graded according to CTCAE v5.0, but they do not influence CRS grading.

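### The Grade 2 CRS management bullet admits low-dose single-vasopressor hypotension that Tables 10 and 15 grade as 3, loosening the re-dosing and recurrence rules for any site that follows it

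*Protocol*

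**What the plan says.** **Grading.** Protocol 11.3.1, Appendix C and SAP 11.1 all grade CRS by the ASTCT consensus scale. In Table 10 and its copy, Table 15, Grade 2 hypotension is hypotension without vasopressors. The Grade 3 cell reads "Requiring a vasopressor with or without vasopressin", with no dose threshold. Footnote b to both tables gives an example: a febrile patient with "hypotension requiring 1 vasopressor, and hypoxia requiring low-flow nasal cannula is classified as grade 3 CRS".

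**Management.** Section 11.3.3.3 sets out what to do by grade. Its Grade 2 entry says that hypotension that responds to fluids or "a low dose of a single pressor, or mild respiratory symptoms treatable with low-flow oxygen are signs of Grade 2 toxicity". Appendix C repeats the entry, again opening with "Hypotension responsive to fluids or a low dose of a single pressor".

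- Grade 2 rules: the infusion is halted. Then, "Once symptoms have resolved, slow the infusion rate by 50% of the baseline rate". If symptoms stay away for an hour and vital signs are stable, "the infusion rate may be increased every 30 minutes, as tolerated, to the baseline rate". For later doses, "Subjects with maximum Grade 2 infusion reaction may continue on study", with premedication. No limit on recurrence is given.
- Grade 3 and 4 rules: "Stop the infusion and disconnect the infusion tubing from the subject". The sponsor's monitor is notified immediately, and ADA samples are taken at onset, at resolution and at 28 days. A resolved Grade 3 event may be rechallenged, but a recurrent one ends XmAb18087.

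**Link to dosing.** For study-drug adjustment and discontinuation after CRS, Section 10.3.1 refers to Section 11.3.3 or Appendix C. The same section has a general rule for AESCs: the same AESC-level event on two consecutive infusions leads to treatment one dose level lower.

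**The concern.** The same clinical event gets two grades a few pages apart, and the grade decides what happens to the drug. The bullet cannot be set aside as applying only to hypersensitivity: it sits under a CRS heading, and 11.3.3.3 says that both kinds of reaction are covered because they are hard to tell apart.

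The event is foreseeable. The protocol expects CRS. Section 11.3.3.2 caps the fluid bolus for acute hypotension at 500 mL and then prefers tocilizumab, with vasopressors if necessary, to more fluid.

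The main stake is re-exposure, in the same session or after a recurrence, of a subject whose CRS has just needed a vasopressor. A lesser stake is the AESC count. CRS is not among the exceptions to the Grade 3 or higher nonhematological criterion in Section 7.8, so a site grading from the bullet could drop an event that Section 7.7 uses to expand a run-in cohort or convene the SRC.

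**Working it through.** **One event, two readings.** Take CRS with hypotension needing a low dose of one vasopressor.

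| Step | Read from the bullet (Grade 2) | Read from Tables 10/15 (Grade 3) |
|---|---|---|
| During the infusion | Halted; may restart at reduced rate once symptoms resolve | Stopped and tubing disconnected |
| Immediate notice to sponsor's monitor; event-driven ADA samples | Not required | Required |
| AESC by grade (7.8) | No | Yes |
| Later doses after a first event | Allowed | Allowed once resolved |
| After a second event | Allowed with premedication | Permanent stop (11.3.3.3), or one dose level lower (general rule, 10.3.1) |

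Resolution of symptoms is a condition in both columns. After a first event, the dosing difference is therefore only the same-session restart.

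**Dose left open after a second event.** Assume events on Day 1 and Day 8 in Part A or C, with no other delay or reduction. These are the first dose and the first escalated dose, where 11.3.2 says CRS is more likely. Doses in µg/kg are from Tables 2 and 4. The remaining Cycle 1 doses are those on Days 15, 22, 29 and 36.

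- 1A/1C: planned 0.3 + 5 × 1.0 = 5.3; remaining 4 × 1.0 = 4.0; 4.0/5.3 = 75.5%
- 2A/2C: planned 0.3 + 1.0 + 4 × 2.0 = 9.3; remaining 4 × 2.0 = 8.0; 8.0/9.3 = 86.0%
- 3A/3C: planned 0.3 + 1.0 + 2.0 + 3 × 4.0 = 15.3; remaining 2.0 + 3 × 4.0 = 14.0; 14.0/15.3 = 91.5%

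The bullet permits all of the remaining dose. The recurrence stop in 11.3.3.3 permits none, so the gap is at most 75% to 92% of the Cycle 1 plan.

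**If the general rule in 10.3.1 is applied instead.** In Parts A and C, Days 1 and 8 are consecutive infusions, and a Grade 3 event meets the AESC criterion. Dosing would then continue one level lower. The protocol does not spell out the step-down in mid-escalation, so two assumed versions show the range.

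- Every remaining dose at 0.3, the next dose below 1.0 in the tables: 4 × 0.3 = 1.2 remains. The gaps are (4.0 − 1.2)/5.3 = 53%, (8.0 − 1.2)/9.3 = 73% and (14.0 − 1.2)/15.3 = 84%.
- The next lower cohort's schedule (0.3 throughout below 1A/1C): 1.2, 4.0 and 8.0 remain. The gaps are 2.8/5.3 = 53%, 4.0/9.3 = 43% and 6.0/15.3 = 39%.

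The gap stays positive on every reading. Its size depends on which rule prevails, and the protocol does not say.

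**The case against.** The strongest reply is that the grade is not in doubt. ASTCT is the stated scale, so a careful site records Grade 3 and follows the Grade 3 rules. Section 11.3.2 says to contact the Medical Monitor immediately with any question about grade or treatment. Section 11.3.1 leaves most CRS management to site procedures and makes the by-grade text a fallback. The tocilizumab and fluid guidance (11.3.3.1, 11.3.3.2) applies whatever the grade. Subjects are inpatients for doses 1 and 2, with at least 24 hours of further monitoring after CRS symptoms subside (7.1).

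All of this stands and lowers the risk. It does not make the texts agree. The monitor helps only if the site notices the conflict, and the fallback status does not reach the discontinuation rule, which 10.3.1 takes from this text.

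Some stronger readings do not hold:

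- A reader might infer that the protocol officially grades such events as 2. It does not; the recorded grade should be 3.
- A reader might infer that Grade 3 certainly means no drug after Day 8. The step-down rule in 10.3.1 competes with that.
- A reader might work out how soon full infusion rate returns after a restart. The infusion duration is blacked out, so neither that time nor the drug still to be infused can be known. Since 11.3.2 says CRS may begin somewhat later, some events may leave no infusion to restart.
- A reader might see a rival scale in 7.8, which names a revised CRS grading system with a 2014 source. Its pointer to Section 11.2 is wrong, but it also points to Appendix C, which holds the ASTCT table. This is mainly a wrong label.

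**Conclusion.** The inconsistency is real and worth correcting. A site that follows the Grade 2 bullet for single-vasopressor CRS could restart XmAb18087 in the same session, would have no recurrence stop, would miss the Grade 3 disconnection, notification and ADA steps, and might leave the event out of the AESC count.

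The size is bounded. After a first event, later doses are open either way. After a second, the difference is at most 75% to 92% of the planned Cycle 1 dose, and less if 10.3.1's step-down governs. These figures rest on the assumed Day 1 and Day 8 events and apply to Parts A and C only. The documents give no frequency for CRS needing one low-dose vasopressor. Realized impact was small: SAP 5.1 reports 2 subjects in Part A and 2 in Part C before termination. Confidence is high in the contradiction and lower in the dosing consequence, which depends on how a site resolves it.

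**What to change.** 1. In 11.3.3.3 and Appendix C, state that any vasopressor use for CRS is at least Grade 3 under Tables 10 and 15 and follows the Grade 3 rules. Remove the low-dose single-pressor clause from the Grade 2 bullet as it applies to CRS. Say that non-CRS reactions remain graded by CTCAE v5.0, since deleting the clause outright would also change the guidance for hypersensitivity.
2. State that the stop for recurrent Grade 3 CRS takes precedence over the one-level reduction in 10.3.1.
3. As clerical corrections, name the ASTCT scale in 7.8, 7.9.1.1 and 7.9.3.1; point 7.8 to 11.3.1 (Table 10) or Appendix C (Table 15); and change the Section 11.2 pointer in 10.1.3 to 11.3.3.

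The cost is a few lines of text, with no added subjects or procedures. As the trial has ended, the wording matters mainly for any protocol that reuses it. For this study, check any CRS grades for the 4 subjects against Table 10 before the listings are final, because SAP 11.1 reports ASTCT grades.
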